6.4 Replacements

Subjects who drop-out will not be replaced.

7 Visit Schedule, Study Procedures, Training & Data Collection

7.1 Visit Schedule

The study consists of the following visits:

Visit 1 – Baseline In office
 Visit 2 – Week 1 Phone Call
 Visit 3 – 12 weeks In office

Visit 4 – 24 weeks
 In office
 Final Visit

Visit 5 - 2-5 days after Final Visit
 Phone Call in case of ongoing AEs at Visit 4, only

Please refer to the overall Schedule of Assessments and the below details for each study visit.

7.2 Visit 1 - Baseline (Day 1)

Study procedures include the following assessments:

- Obtain written informed consent
 - Parents/caregivers will sign the Informed Consent
 - o 18 year old child with diabetes will sign informed consent
 - o Children with diabetes will sign age-appropriate assent form
- Check eligibility of Inclusion and Exclusion criteria
- Child/adolescents with diabetes: Perform urine pregnancy test (menstruating females)
- Child/adolescent with diabetes and parents/caregivers: Smartphones; see section 6
- Collect/document the following parameters:

Information on the child/adolescent with type 1 diabetes

- o Demographics (age/gender/race/ethnicity)
- Obtain and record Diabetes Background and History including insulin therapy, use of CGM, current diabetes devices, use of diabetes management software and Apps, SMBG habits and frequency
- Obtain and record Diabetes Medication, total daily basal dose and average number of boluses per day, sensitivity factors, insulin-to-carb-ratio and target point/range.
- Identify Diabetes Management responsibility (parent/caregiver primarily managing, child self-managing, or child currently transitioning to self-management
- o Communication regarding diabetes parents/caregiver when at school
 - Method: (phone/email/text)
 - Frequency: (multiple times/day, daily, weekly, as needed for problem resolution only).

Information on parent(s)/caregiver(s)

o Demographics (age/gender/race/ethnicity/education/job- and marital status)

- o Any software, devices or Apps used to monitor child with diabetes remotely
- o Communication regarding diabetes with child when at school
 - Method: (phone/email/text)
 - Frequency: (multiple times/day, daily, weekly, as needed for problem resolution only)
- o Communication regarding diabetes with school staff
 - Method: (phone/email/text)
 - Primary Contact: (school nurse, teacher, or other school staff)
 - Frequency: (multiple times/day, daily, weekly, as needed for problem resolution only)
- Collect height and weight
- Obtain capillary (finger-stick) blood sample for determination of HbA1c (at central laboratory)
- Administer Questionnaires
 - o Intervention Sites: prior to training in the use of ACCU-CHEK® Connect DMS
 - Control Site(s): prior to general study instructions
- Record brand of current BG meter and serial number
- Download SMBG data using existing site process and discuss SMBG download with patient and parent/caregivers and collaboratively agree on therapy changes (pharmacologic and/or behavioral) and modify SMBG regimen, if needed.
- Download current BG meter using Diasend for eCRF data
- Schedule appointment for week one phone call (Visit 2) and 3 months (Visit 3)
- Record number of days missed from work (parent/caregiver)/school (child with diabetes) that
 are diabetes related in previous 3 months and indicate reason (doctor appointments, illness or
 other.
- Discuss and record current prescribed therapy (pharmacologic and/or behavioral) and prescribed SMBG regimen.
- Record any adverse events (AEs) since last visit if not done immediately
- Record all relevant data in the eCRF

Intervention Sites, only

- Dispense ACCU-CHEK[®] Connect DMS and record serial number of BG meter(s)
- Dispense Smartphone to child/adolescent (if applicable)
- Set up ACCU-CHEK[®] Connect DMS for connectivity, portals & invitations
- Provide training in the use of the system
- register current operating system of smart phone with version number
- Dispense Call Center Card and instruct in reporting of malfunctions/complaints with ACCU-CHEK® devices

7.3 Visit 2 – Phone Call one week after Visit 1

Study procedures include the following assessments:

- Record any adverse events (AEs) since last visit, if this has not been done immediately
- Record malfunctions/complaints of any device, if any
- Intervention group: Follow-up with parents/caregivers and child with diabetes to identify issues/obstacles associated with system in use
- Record all relevant data in the eCRF

7.4 Visit 3 - 12 weeks after Visit 1

Study procedures include the following assessments:

- Record any malfunctions/complaints, of device as applicable
- Assess and record any new AE, if this has not been done immediately and/or changes to ongoing AE/SAEs since the previous visit.
- Download child's BG data and review
 - o Intervention Sites: review ACCU-CHEK Connect Diabetes Management data
 - Control Site(s) review usual care SMBG data
- Discuss SMBG download with patient and parent/caregivers and collaboratively agree on therapy changes (pharmacologic and/or behavioral) and modify SMBG regimen, if needed.
- Discuss any change in software, devices, or apps used to manage diabetes or monitor child w/diabetes remotely
- Collect height and weight
- Record number of (diabetes related) days parents/caregivers missed from work and child with diabetes missed from school since last visit; indicate reason (doctor appointments, illness or other)
- Obtain capillary (finger-stick) blood sample for determination of HbA1c (at central laboratory)
- Intervention Group: Follow-up with parents/caregivers and child with diabetes to identify issues/obstacles associated with system in use
- Control Group: Download current BG meter using Diasend for eCRF data
- Have child and his/her parents complete Questionnaires
- Make appointment for the last Visit, Visit 4 6 months after Visit 1
- Record all relevant data in the eCRF

7.5 Visit 4 - Final Visit - 24 weeks after Visit 1

Study procedures include the following assessments:

Record any malfunctions/complaints, of any device as applicable

- Assess and record any new AE/SAEs and/or changes to ongoing AE/SAEs since the previous visit.
- If ongoing AE/SAE; schedule appointment for a Follow-up call in 2-5 days
- Download child's BG data and review
 - o Intervention Sites: review ACCU-CHEK Connect Diabetes Management data
 - o Control Site(s) review usual care SMBG data
- Discuss and record any therapy changes (pharmacologic and/or behavioral) and modify SMBG regimen, if needed.
- Discuss any change in software, devices, or apps used to manage diabetes or monitor child w/diabetes remotely
- Collect height and weight
- Record number of (diabetes related) days parents/caregivers missed from work and child with diabetes missed from school since last visit; indicate reason (doctor appointments, illness or other)
- Obtain capillary (finger-stick) blood sample for determination of HbA1c (at central laboratory)
- Intervention Group: Follow-up with parents/caregivers and child with diabetes to identify issues/obstacles associated with system in use
- Control Group: Download current BG meter using Diasend for eCRF data
- Have child and his/her parents complete Questionnaires
- Have child/parents/caregivers return smartphones, if these had been provided at the beginning of the study
- Record all relevant data in the eCRF

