7.7 Unscheduled Study Visits or Phone Calls

During the course of the study, subjects may require additional (unscheduled) visits with their physicians (Investigators) for any number of reasons including, but not limited to the following:

- Diabetes medication/therapy adjustments
- Assess whether ACCU-CHEK[®] Connect data provided by the patient was sufficient to make informed decisions regarding patient therapy adjustment.
- Adverse Events such as, but not limited to:
 - o Common respiratory infections including colds and flu.
 - Urinary tract infections.
 - o Gastrointestinal disturbances.
 - o Depression.
 - Minor injuries.

For tracking purposes and future analysis of the potential cost effectiveness, any additional study visits will be documented as **Unscheduled Visits** in the electronic case report form (eCRF).

Any conditions like above should be documented under Adverse Events.

Any changes to medication should be documented, as follow:

• Insulin (any changes in doses or parameters) under Diabetes Medication

Full documentation of the visit including any assessments or examinations performed should be maintained in the source documents; including:

- Person requesting unscheduled visit
- Reason for unscheduled visit
- If visit is remote or in-office
- Type of remote visit (i.e. telephone, email, text, video chat, etc.)
- Action taken during consult
- Source of data utilized for consult (i.e. electronically sent reports, web portal, verbal, etc.)
- Therapy/device/SMBG changes made as a result of remote visit
- Any change in software, devices, or apps used to manage diabetes or monitor child w/diabetes remotely

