7.8 Training of Subjects

In order to prepare subjects as well as their parents/caregivers for the study procedures, they will be trained at the Baseline Visit (Visit 1) in the following:

Intervention Group:

The children with diabetes as well as their parents/caregivers will be trained in the following:

- use and functionalities of the ACCU-CHEK® Connect DMS.
- reporting of malfunctions/complaints via the Call Center
- general study procedures

Control Group:

The children with diabetes as well as their parents/caregivers in this group will only be trained in general study procedures, as the children continue to use their previous diabetes management system.

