5.6 Safety Analyses

The patient incidence of adverse events will be summarized by intervention group, MedDRA System Organ Class and Preferred Term. Such summaries will be displayed for all AEs, AEs by maximum severity, AEs by strongest causality to study device (and any associated pump devices), and AEs leading to withdrawal of study device. A separate analysis of the patient incidence of symptomatic hypoglycemia, severe hypoglycemia (SAE), and diabetic ketoacidosis (SAE) will also be presented.

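### At Visits 2, 3 and 4 only intervention families get an extra follow-up on problems with their system, so the descriptive by-arm adverse event summary may partly reflect unequal ascertainment

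*Protocol*

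**What the plan says.** **Common to both arms.** At Visit 2 (Protocol 7.3) the AE item is "Record any adverse events (AEs) since last visit, if this has not been done immediately" and the device item is "Record malfunctions/complaints of any device, if any". At Visit 3 (7.4) the AE item is "Assess and record any new AE, if this has not been done immediately and/or changes to ongoing AE/SAEs since the previous visit", and Visit 4 (7.5) has a similar one. Both visits also list malfunctions and complaints. The rows for these items in the Schedule of Assessments carry no intervention-only footnote.

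**Intervention arm only.** Visit 2 adds the item "Intervention group: Follow-up with parents/caregivers and child with diabetes to identify issues/obstacles associated with system in use". The same item stands under both 7.4 and 7.5: "Intervention Group: Follow-up with parents/caregivers and child with diabetes to identify issues/obstacles associated with system in use". No matching item about the current system is listed for controls. Under 7.8 intervention families are trained to report malfunctions and complaints through the Call Center, while control families "in this group will only be trained in general study procedures".

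**Unscheduled visits.** Protocol 7.7 gives several reasons for such visits. One is to judge whether Connect "data provided by the patient was sufficient to make informed decisions regarding patient therapy adjustment". Conditions of the kind listed there are to be documented as AEs.

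**Analysis.** SAP 5.6 states: "The patient incidence of adverse events will be summarized by intervention group, MedDRA System Organ Class and Preferred Term". It adds a separate analysis of symptomatic hypoglycemia, severe hypoglycemia and diabetic ketoacidosis. Neither document provides for recording, AE by AE, how the event came to light.

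**The concern.** A by-arm AE table can be read as a comparison only if events had about the same chance of being noticed in each arm. Here one arm has an additional conversation with parent and child at each of the three visits.

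The conversation is about the system, but it can lead to AEs by two routes. Symptomatic hypoglycemia is a captured AE defined by symptoms, and a glucose reading may confirm it but need not (Protocol 9.2.2, 9.3.1.1). A family describing a difficulty with the meter or app may mention such an episode. In addition, AEs that result from user error or inadequate instructions are classified as device related (9.4.1). A talk about obstacles is where these would surface, so the causality table could be affected as well as the incidence table.

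Whole sites are assigned to an arm and no masking is described, so families and staff know the assignment. Extra events in the Connect arm could then be partly an artefact of asking, and a true reduction could be partly hidden.

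**Working it through.** **The plan's own figure.** The only design figure given is for the primary endpoint (Protocol 11.1, SAP 2.1.2): 75 per group, 80% power, effect size 0.460, two-sided 5%. It reproduces. The normal approximation gives n = 75 with power 80.4% (79.9% by the noncentral t), and 0.460 × 5 = 2.3 and 0.460 × 16 = 7.36. It does not bear on AEs. The documents state no AE rate, AE hypothesis or AE power.

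**Contacts compared by arm (Protocol 7.3 to 7.6).**

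| Contact | New AEs collected | AE item | Malfunction/complaint item | System follow-up |
|---|---|---|---|---|
| Visit 2 | yes | both arms | both arms | intervention only |
| Visit 3 | yes | both arms | both arms | intervention only |
| Visit 4 | yes | both arms | both arms | intervention only |
| Visit 5 | no, only AEs ongoing at Visit 4 | both arms | none | none |

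The asymmetry is present at 3 of the 3 scheduled post-baseline contacts that collect new AEs, and at 3 of 4 if Visit 5 is counted.

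**Possible size, on assumed inputs.** Let p be the true incidence, equal in both arms, and let c1 and c0 be the probability that an affected subject's event is recorded in the intervention and control arms. Then

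- reported incidence = p × c1 and p × c0
- apparent risk ratio = c1 / c0, which does not depend on p
- apparent risk difference = p × (c1 − c0)

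None of p, c1 or c0 is in the documents. With c1 = 0.90 assumed:

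| c0 | Risk ratio | Reported at p = 30% | Difference | Reported at p = 50% | Difference |
|---|---|---|---|---|---|
| 0.90 | 1.00 | 27% vs 27% | 0 points | 45% vs 45% | 0 points |
| 0.80 | 1.125 | 27% vs 24% | 3 points | 45% vs 40% | 5 points |
| 0.70 | 1.29 | 27% vs 21% | 6 points | 45% vs 35% | 10 points |
| 0.50 | 1.80 | 27% vs 15% | 12 points | 45% vs 25% | 20 points |

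With the planned 100 enrolled per group, each point is one subject. The first row is the case in which the follow-up adds no AE reports.

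**The case against.** The strongest reply is that AE elicitation itself is the same. The AE items do not differ by arm, and at each visit they are listed before the system follow-up, which concerns the system and not symptoms. Controls are also asked about malfunctions or complaints at all three visits. At Visits 3 and 4 both arms review glucose data, discuss changes in devices or apps, and report missed school and work days with reasons that include illness. This stands. A reader might infer that controls get the AE question alone, or that the plan elicits AEs more intensively in one arm; the documents support neither. More AE reporting from the extra conversation is an inference. However, the order of a list is not a stated rule on sequence, and a malfunction item is narrower than an open question about obstacles.

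The supporting routes are weak. The Call Center takes malfunctions and complaints (Protocol 10), while AEs are recorded by the site in the eCRF. Section 7.7 applies to both arms, its Connect item concerns whether data sufficed, and it already requires source notes on who asked for the visit and why. These routes add little beyond the three-visit asymmetry.

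Finally, no between-arm AE test is planned. SAP 5.6 and Protocol 11.6 call for summaries only, so a false-positive rate would belong to an analysis that is not in the plan. This also stands, although a table by arm still invites a by-arm reading.

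A separate matter affects the same table more directly. Protocol 11.6 limits AE tables to events after the start of the Connect online system, which controls never start. That needs its own reconciliation with SAP 5.6.

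**Conclusion.** The point holds as a possible difference in ascertainment. At every scheduled post-baseline contact that collects new AEs, one arm has an extra system follow-up, and the descriptive by-arm AE summary may partly reflect this. The conclusion rests on the open design, on self-reported hypoglycemia being a captured AE, and on user-error events counting as device related.

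The size cannot be computed from the documents. The ratios of 1.00 to 1.80 follow from assumed capture probabilities and show scale only, and zero is within the range. A reader might conclude that the AE comparison is biased, or that every post-baseline AE contact is affected. The first is not shown, and Visit 5 contradicts the second. The primary endpoint and the sample size are untouched. This is a cheap improvement to a descriptive safety output.

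**What to change.** **Protocol 7.3 to 7.5.** State that the AE item is completed first in both arms. Then ask both arms the same device-neutral question about issues or obstacles with the glucose monitoring system in use.

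**eCRF.** Add one field for how each AE came to light: scheduled AE question, system follow-up, immediate or spontaneous report, unscheduled contact, or Call Center.

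**SAP 5.6.** Keep all AEs and SAEs, including those reported immediately, in the main by-arm table. Add a supplementary table that breaks AEs down by source or leaves out those first raised in the system follow-up. The main table should not be restricted to events from the scheduled AE question. The items at Visits 2 and 3 pick up only what has not already been recorded, and SAEs go in at once (Protocol 9.6). Severe hypoglycemia and diabetic ketoacidosis, both SAEs under 9.2.3 and 9.2.5, would tend to drop out.

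**Cost.** One short question for controls at contacts they already have, one eCRF field and one extra table, with no added visits. Controls are already asked about device malfunctions, so the question sits easily with the aim in Protocol 2.1 of leaving control behavior unchanged. The source field should be in place before the visits, because how an event surfaced is hard to reconstruct later.

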7.6 Visit 5 - Follow-up Call

This follow-up phone call takes place 2-5 days after the study end. Study procedures include the following:

- Assess and record any changes to AE/SAEs which were ongoing at Visit 4 (Final Visit).
- Record all relevant data in the eCRF

7.7 Unscheduled Study Visits or Phone Calls

During the course of the study, subjects may require additional (unscheduled) visits with their physicians (Investigators) for any number of reasons including, but not limited to the following:

- Diabetes medication/therapy adjustments
- Assess whether ACCU-CHEK[®] Connect data provided by the patient was sufficient to make informed decisions regarding patient therapy adjustment.
- Adverse Events such as, but not limited to:
 - o Common respiratory infections including colds and flu.
 - Urinary tract infections.
 - o Gastrointestinal disturbances.
 - o Depression.
 - Minor injuries.

For tracking purposes and future analysis of the potential cost effectiveness, any additional study visits will be documented as **Unscheduled Visits** in the electronic case report form (eCRF).

Any conditions like above should be documented under Adverse Events.

Any changes to medication should be documented, as follow:

• Insulin (any changes in doses or parameters) under Diabetes Medication

Full documentation of the visit including any assessments or examinations performed should be maintained in the source documents; including:

- Person requesting unscheduled visit
- Reason for unscheduled visit
- If visit is remote or in-office
- Type of remote visit (i.e. telephone, email, text, video chat, etc.)
- Action taken during consult
- Source of data utilized for consult (i.e. electronically sent reports, web portal, verbal, etc.)
- Therapy/device/SMBG changes made as a result of remote visit
- Any change in software, devices, or apps used to manage diabetes or monitor child w/diabetes remotely

7.8 Training of Subjects

In order to prepare subjects as well as their parents/caregivers for the study procedures, they will be trained at the Baseline Visit (Visit 1) in the following:

Intervention Group:

The children with diabetes as well as their parents/caregivers will be trained in the following:

- use and functionalities of the ACCU-CHEK® Connect DMS.
- reporting of malfunctions/complaints via the Call Center
- general study procedures

Control Group:

The children with diabetes as well as their parents/caregivers in this group will only be trained in general study procedures, as the children continue to use their previous diabetes management system.

7.9 Questionnaires

Children with diabetes and their parents/caregivers will be asked to complete the following Questionnaires:

- Visit 1 (Intervention group to complete prior to receiving training for ACCU-CHEK® Connect DMS):
 - o Parents/Caregivers (independently of age of the child)
 - PAID Parent to Child or Teen dependent on age of child with diabetes
 - BGMC parent
 - DFCS parent
 - o Adolescent/Teen with diabetes (12-18y)
 - PAID Teen
 - DFCS youth
 - BGMC youth
 - o Child with diabetes (8-11y)
 - PAID Child
 - DFCS youth
 - BGMC youth
- Visit 3:
 - Parents/Caregivers (independently of age of the child)
 - PAID Parent to Child or Teen dependent on age of child with diabetes
 - BGMC parent
 - DFCS parent
 - Adolescent/Teen with diabetes (12-18y)
 - PAID-Teen
 - DFCS youth
 - BGMC youth

- o Child with diabetes (8-11y)
 - PAID Child
 - DFCS youth
 - BGMC youth
- Visit 4:
 - o Parents/Caregivers (independently of age of the child)
 - PAID Parent to Child or Teen -(dependent on age of child with diabetes)
 - BGMC parent
 - DFCS parent
 - Questionnaire about Use, Preference, Satisfaction (Intervention Group Only)
 - o Child/Adolescent/Teen with diabetes (12-18y)
 - PAID Teen DFCS youth
 - BGMC youth
 - Questionnaire about Use, Preference, Satisfaction (Intervention Group Only)
 - o Child with diabetes (8-11y)
 - PAID Child
 - DFCS youth
 - BGMC youth
 - Questionnaire about Use, Preference, Satisfaction (Intervention Group Only)

Healthcare Providers, School Staff of the intervention group will be asked to complete the Questionnaires about Use, preference, Satisfaction

All Questionnaires will be completed through the eCRF set-up in the Marvin-system; see section 7.11.

7.10 Central Laboratories

Central lab will be utilized for the determination of:

HbA1c at Visit 1, 3 and 4.

For details regarding tubes, labeling, packaging, dispatch to central laboratory, please refer to the Central Laboratory Handbook.

7.11 Data Collection

A **Subject Screening and Enrolment Log** will be completed for all subjects whose parents/caregivers have provided their informed consent i.e., signed the Informed Consent Form - with the reasons for non-eligibility, if applicable.

eCRF

An eCRF has been set up in the Marvin system, provided by

For each subject who has signed the Subject Informed Consent Form, the Investigator must allocate a **subject ID number** via the eCRF-system of two digits for the site and three digits for the subject: **SS-XXX**.

For each enrolled subject, an eCRF must be completed (throughout the study) and electronically signed by the Principal Investigator or Sub-/ Co-Investigator (at the end of the subject's participation in the study).

Upon training, Investigators and authorized study staff will enter subject data during or shortly after the respective visits.

Data Discrepancy Management

Subsequently, the entered data will be systematically checked:

- by means of pre-defined computerized validation checks (as outlined in the Data Management Plan)
- by data review by the Sponsor including but not limited to the Data Manager, Monitor and Study Manager.

All data discrepancies will result in data queries within the eCRF-system, which must be addressed (data confirmed or changed) by the study site staff and closed by the originator.

In addition, protocol violations and deviations must be recorded in the eCRF throughout the study, and documented further via the query-system, as applicable (see Section 14).

If a subject withdraws from the study, the reason must be recorded on the eCRF.

Subject and Parent/Caregiver Questionnaire

Subjects and their parents/caregivers will be asked to complete a questionnaire at Visits 1, 3 and 4, see Section 7.9. These questionnaires will be presented via the site's provided study laptop.

At the first login, the subject is asked to define and enter a new password.

As soon as the subject has completed the questionnaire(s), he/she should close the entry screen by clicking the red "Log-out" button at the upper right corner.

For the sake of confidentiality, neither the Investigator nor other study staff will be able to read the subject's entries.

HCP and School Nurse Staff Questionnaires

For Intervention Group sites only, the HCP (Site Investigator and School Nurse/staff (if available)) will be asked to complete to complete a Questionnaire.

Measures arising from sources other than questionnaires

Glycemic Control: HbA1c levels - at Baseline, visit 3 and 4 - analyzed by central lab

- Data from ACCU-CHEK® Connect BG-meters:
 - o Change in SMBG habits and frequency (Baseline and Visit 4)
 - Percentage in Glucose Target Range, above and below Glucose Target Range
 - o Glycemic Variability
 - Hypoglycemia
- Data from ACCU-CHEK® Connect DMS and eCRF entries:
 - Assessment by HCP whether Accu-Chek Connect data provided by the patient was sufficient to make informed decisions regarding patient therapy adjustment.

SMBG data and other diabetes-related data from ACCU-CHEK® Connect system is planned to be uploaded into the eCRF during the study and after study completion. The mapping of these device data to the correct subject with diabetes will be an automated de-identification process for saving the device data with the subject data.

Database Closure

Quality control of the database will be made throughout the study conduct in order to prepare the database closure. After the database has been declared clean (i.e. complete and accurate), the database will be locked.

Any changes to the database after that time can only be made by joint written agreement between the Study Manager and the Statistician.

